In addition, the 2006 consensus guidelines for management of abnormal cytology and histology were updated. For women under 26 years of age with abnormal cytology and histology, observation with cytology and colposcopy is recommended over invasive treatments such as LEEP and cryotherapy. More specifically, for young women with ASCUS and LSIL, it is recommended to repeat cytology annually and refer to colposcopy only if persistent at 2 years or if HSIL develops. Recommendations continue from the 2006 guidelines that young women with HSIL (CIN 2,3), defined as those interested in fertility, be followed by colposcopy and cytology rather than immediately referred for therapy.

Adherence to these screening and management guidelines has been disappointingly low, although the adherence to other national guidelines in general is low. Dissemination and implementation of these guidelines can be a challenge in the US--many women equate health care with annual Pap smears and continue to demand these examinations. In addition, many physicians may have financial incentives to over screen and treat or are not aware of current guidelines.

This research will be expected to influence adherence to guidelines and lead to improved patient health and well-being as this study would show interventions that are capable of lowering the number of unnecessary colposcopic examinations, cervical biopsies and excisional therapies. All of these procedures have been shown to have negative effects including psychological distress

and premature delivery. Numerous providers and stakeholders have underscored the need to avoid these unnecessary procedures.

There has been little done regarding physician based interventions regarding cervical cancer screening. In general, message based interventions (i.e., messages on laboratory reports), payment denials, and electronic medical record messages have all been examined with mixed results. Newer technologies have not been evaluated extensively in any setting. These include offering free applications (APPs) for mobile phones, which would give easy access to guidelines. In addition, no mobile application intervention for patient decision-making has been applied for cervical cancer screening.

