## **STUDY METHODOLOGY**

### **Study Intervention**

#### *Choice of Comparators*

We will compare 2 different interventions arms that are designed to prevent overscreening and over treatment by increasing adherence to the new US cervical cancer screening guidelines and the ASCCP guidelines for the management of abnormal cervical cancer screening tests and cancer precursors. Specifically, the interventions will focus on lengthening cervical cancer screening intervals to every 3 years, decreasing colposcopy procedures for minimally abnormal cytology results and decreasing treatment of cervical precancerous lesions with a high rate of regression (i.e., cervical intraepithelial neoplasia grades 2 and 2/3).

The two arms will be:

- 1) Mobile application (APP)-based intervention for providers,
- 2) Mobile application (APP)-based intervention for providers PLUS patient-centered approach intervention (PCA).

The two arms will be compared to a comparison group (no intervention).

The APP-based intervention (APP) is for clinicians' mobile phones and will maneuver them through current guidelines (cervical cancer screening and management of abnormal cytology and histology) based on patient age and condition. This is the current ASCCP tool, which will be updated to include screening guidelines and risk assessment so the provider can better understand the risk associated with follow-up versus premature triage to colposcopy.

The patient-centered approach intervention (PCA) is oriented towards educating women about HPV and cervical cancer screening. The intervention will be provided to patients' when they check-in for a clinic appointment, and will interactively provide information designed to help them understand current guidelines for the frequency of cervical cancer screening and appropriate management for abnormal cytology and treatment options. It will allow them to assess the risks and benefits of screening intervals and of treatment choices.

Comparison sites will have no intervention.

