### *Development of the PCA Intervention*

Four focus groups will be held both English and Spanish speaking, separately. With the assistance of NCCC and LCC, our patient stakeholders women aged 21-29 years of age will be identified for each focus group (See **Appendices A & B** for Focus Group Scripts). The focus groups will review the guidelines and their rationale and ask women what messages would be most appropriate and acceptable to the target population. Women with cancer, CIN and no abnormal cervical cytology will be targeted for inclusion whenever possible. Women who have never been screened for cervical cancer also will also be sought to participate. Issues that will be addressed include fears, concerns, and areas of uncertainty she may have around screening, and potential messages that could be used to address these issues. Thematic areas will focus on: cervical cancer screening intervals in young women under 30 years; natural history of HPV, follow-up of ASCUS and LSIL cytology by cytology only in women aged 21-24 years vs. immediate referral to colposcopy, follow-up of biopsy proven LSIL by cytology without treatment, follow-up of biopsy proven HSIL by colposcopy and cytology vs. immediate treatment, treatment options (cryotherapy vs. excisional therapy).

Transcriptions of the oral discussions of the focus groups will be taken and distributed to the group. Based on the transcriptions, we will develop a paper tool.

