### **Sample Size Estimates and Power Calculations**

The database for FY 2010/11 shows that 386 clinics fit the criteria with 89 sites available for arms 1-2 and 297 available for the comparison group. The mean number of female clients aged 21-29 years seen at the eligible clinics was 560 and the mean number of cytology specimens, colposcopic examinations and LEEP/cryoprocures for this age group was 297, 40, and 4, respectively. In 2012, the mean cytology interval was 19 months. Very few clinics had an interval >30 months. There were no differences for any of the above variables between those

sites eligible for intervention and those for comparison. These numbers have not changed significantly in the past 2 years and will be updated for the baseline assessment.

After enrolling 7 sites into each arm, we estimate that we would have approximately 2800-3500 women aged 21-29 years in each arm. For each arm, baseline cytology rate in this age group would be approximately 50%, rate of colposcopy procedures for those who had cytology would be 13%, and rate of LEEP/cryotherapy procedures for those referred to colposcopy would be 10%.

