**b) To increase average length of cervical cytology testing among women under 30 years of age**

**Pre:** cervical cytology test interval among women who received two CC tests from same provider (analysis limited to providers who have been in program at least 36 months)

**Post:** cervical cytology test interval among women who received their second CC test 3-15 months after the intervention started.

**c)** To decrease the number of LEEP and cryotherapy procedures in women under 30 years of age with abnormal cytology.

**Pre:** Rate of women 21-29 years of age who receive LEEP or cryotherapy over total number of women 21-29 years of age in quarter before intervention started.

**Post:** Rate of women 21-29 years of age who receive colposcopy or LEEP or cryotherapy over total number of women 21-29 years of age in 3-6, 9-12, and 15-18 months after intervention started.

**d)** To decrease the number of colposcopy procedures in women 21-24 years of age with abnormal cytology.

**Pre:** Rate of women 21-24 years of age who receive colposcopy over total number of women 21-24 years in quarter before intervention started.

**Post:** Rate of women 21-24 years who receive colposcopy over total number of women 21-24 years of age in 3-6, 9-12, and 15-18 months after intervention started.

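### Endpoint (d) counts any colposcopy at ages 21-24, so follow-up colposcopies done in place of treatment can dilute a real fall in referrals and could cancel a modest one

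*Combined protocol and SAP*

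**What the plan says.** - **Endpoint.** Data Analyses, item (d), takes as its baseline "Rate of women 21-24 years of age who receive colposcopy over total number of women 21-24 years in quarter before intervention started" and as its outcome "Rate of women 21-24 years who receive colposcopy over total number of women 21-24 years of age in 3-6, 9-12, and 15-18 months" after the start of the intervention. The title of the item refers to abnormal cytology, but neither numerator nor denominator is limited by cytology result or by reason for the colposcopy.
- **Aim.** Choice of Comparators describes the colposcopy target as "decreasing colposcopy procedures for minimally abnormal cytology results". The same sentence sets a second target, less treatment of CIN 2 and 2/3.
- **Guideline.** Screening and Management Guidelines gives advice that works in both directions. For ASCUS and LSIL in young women, "it is recommended to repeat cytology annually and refer to colposcopy only if persistent at 2 years or if HSIL develops", which means fewer referrals. For women under 26 with abnormal cytology and histology, "observation with cytology and colposcopy is recommended over invasive treatments such as LEEP and cryotherapy". Young women with HSIL who are interested in fertility are to "be followed by colposcopy and cytology rather than immediately referred for therapy".
- **Tools.** Development of the PCA Intervention lists "follow-up of biopsy proven HSIL by colposcopy and cytology vs. immediate treatment" among the focus-group themes. The provider app section says that risk assessment will help with the choice between treating and watching.
- **Analysis.** Neither Data Analyses nor the sensitivity section separates referral from follow-up colposcopy, or says how items (c) and (d) are to be read together.

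**The concern.** Success on one target can count against the other. A woman aged 21-24 who is observed instead of treated may have one or more further colposcopies, and each window in which she has one adds her to the numerator of (d). The windows start six months apart, so a woman seen every six months could appear in all three.

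Comparing arms does not remove this, because the extra follow-up would itself be an effect of the intervention. The comparison clinics receive none, so their change scores would not cancel it.

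A flat colposcopy rate could then mean no change, or fewer referrals offset by more follow-up. As the number of women under observation grows, the offset grows from window to window, and that could be misread as a fading intervention effect.

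**Working it through.** **Inputs from the plan.** Sample Size Estimates and Power Calculations gives mean counts per clinic at ages 21-29, for cytology, colposcopy and "LEEP/cryoprocures for this age group was 297, 40, and 4, respectively". I take these as annual, since the source is a fiscal-year database.

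**The plan's ratios.** Colposcopy per cytology: 40/297 = 13.5% (stated 13%). Treatment per colposcopy: 4/40 = 10% (stated 10%). Both reproduce.

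**Assumptions not in the documents.**
- The 10:1 ratio also holds at ages 21-24.
- A share *a* of treatments (25% to 100%) is replaced by observation.
- Each observed woman has *v* = 1 or 2 colposcopies a year.
- Nobody leaves observation during the study.
- Treated women would have had no later colposcopy, so the result is a gross figure.

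**Formula.** After *t* years, *a* × 4 × *t* women per clinic are under observation. They add *a* × 4 × *t* × *v*/4 colposcopies in a quarter, against a baseline of 40/4 = 10. So

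offset = 0.10 × *a* × *v* × *t*,

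with *t* at mid-window: 4.5/12 = 0.375, 10.5/12 = 0.875 and 16.5/12 = 1.375.

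| Scenario | Months 3-6 | Months 9-12 | Months 15-18 |
|---|---|---|---|
| *a* = 25%, *v* = 1 | 0.9% | 2.2% | 3.4% |
| *a* = 50%, *v* = 2 | 3.8% | 8.8% | 13.8% |
| *a* = 100%, *v* = 2 | 7.5% | 17.5% | 27.5% |

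**Against the planned effect.** I read the plan's 8% reduction as percentage points, 13% to 5% of women with cytology. With 50% tested at baseline and 20% fewer at follow-up (40%), the rate per woman goes from 0.50 × 13% = 6.5% to 0.40 × 5% = 2.0%, a fall of 4.5/6.5 = 69.2%. The largest offset leaves 69.2 − 27.5 = 41.7%, and the smallest leaves 69.2 − 0.9 = 68.3%. The effect is diluted, not hidden. I use 13% to 5% only as a yardstick. The stated 80% power is a separate matter: a simple cluster-adjusted calculation with the plan's inputs gives about 60%.

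**Against a modest effect.** Express the referral fall as a share of all baseline colposcopies.
- A 10% fall is cancelled when *a* × *v* × *t* = 1. With *v* = 2 this needs *a* = 57% in months 9-12 or 36% in months 15-18.
- A 20% fall is cancelled when *a* × *v* × *t* = 2. With *v* = 2 this needs *a* = 73% in months 15-18, and it is not reached in the earlier windows.

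**Net of follow-up after treatment.** If treated women would have had *u* colposcopies a year, replace *v* by *v* − *u*. With *v* = 2 and *u* = 1, every offset halves.

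**The case against.** The case on the other side is substantial, and much of it stands.

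- **Total burden is a legitimate outcome.** Study Objectives speaks of fewer colposcopy examinations without restriction, and Relevance to Patients describes the distress that colposcopy itself causes. This stands: the all-colposcopy rate should be kept.
- **Size.** Treatments are only a tenth of colposcopies, so dilution is likelier than masking, and full cancellation arises only for effects well below the one planned for. This also stands. A reader might infer that success on treatment raises the overall colposcopy rate; the documents do not show that.
- **Link between (c) and (d).** A reader might infer that every treatment avoided on (c) adds a failure on (d). It does not follow. Item (c) covers ages 21-29 and (d) only 21-24. The post numerator of (c) as written also includes colposcopy, while its pre numerator does not, so a woman moved from treatment to colposcopic follow-up may still count on (c).
- **Only the intervention arms?** That too is more than the text supports. The observation advice for HSIL is said to continue from 2006, and comparison providers may already use the app. Only a differential increase biases the comparison.
- **The tools.** HSIL follow-up is a focus-group theme, and the patient tool's content list has no explicit item on it. The app's worked example concerns LSIL and repeat cytology. How strongly the tools would shift this behaviour is uncertain, although less treatment of CIN 2 and 2/3 is a declared target.
- **Counting.** The endpoint counts women once per quarter, so repeats within a window do not add. Repeats across windows do.

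What remains is that (d) mixes the colposcopies the intervention aims to reduce with those the guideline recommends, and no analysis separates them.

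**Conclusion.** The concern holds as a directional bias in a secondary endpoint. If treatment falls at ages 21-24 and observation replaces it, the measured fall in referrals is diluted. The gross offset is about 1-8%, 2-18% and 3-28% of baseline in the three successive windows, and the net offset is smaller if treated women would also have had later colposcopies. This could cancel a true fall of 10% and, at the upper end of the assumptions in the last window only, one of 20%. It would not hide the planned fall from 13% to 5%.

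The figures rest on the 21-29 ratio, since none is given for 21-24, and on assumed treatment avoidance and visit frequency. The problem of interpretation does not depend on the exact size: as defined, a flat result on (d) cannot tell no change from two offsetting changes. The documents do not support the stronger inference that the endpoint is invalid or that the intervention would push the total rate up.

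**What to change.** Treat this as a cheap improvement, made before outcome data are examined.

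1. Keep the all-colposcopy rate at ages 21-24 as the measure of total burden.
2. Pre-specify its split by a claims look-back applied identically before and after and in all groups. For example, call a colposcopy first (referral) if the woman has no colposcopy or LEEP/cryotherapy claim in the previous 24 months, and repeat (follow-up) otherwise.
3. Base the conclusion about fewer referrals on the first-colposcopy rate, and report repeats descriptively by window.
4. Read (d) together with a treatment-only version of (c), with the same numerator before and after.

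**Cost.** Some wording and a look-back in the claims program. Data Analyses warns that patient-level analysis will be limited, but item (b) already links a woman's successive tests at one provider and requires 36 months in the program, so the linkage needed is of a kind already planned.

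**Downsides.** There will be fewer events. Women with an earlier colposcopy elsewhere, or new to the program, will be misread as first referrals. Study Population reports 74% retained, so about 100 − 74 = 26% of clients, in the program's overall figure, had no use in the prior four years and would have no look-back claims. First colposcopy also still includes referrals that the guideline recommends, so it only approximates the target of minimally abnormal cytology.

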#### *Sensitivity and Heterogeneity of Treatment Effect:*

Each intervention group and the control group will be examined for its sensitivity and heterogeneity by using a jack-knife technique computing the intervention effect leaving out each of the clinics consecutively. The variability of the results of these analyses within intervention will be compared to the overall effect to examine how sensitive the results are to each clinic. Within each clinic, patients with some missing data will be included and then excluded from the summary analyses of that clinic and intervention to examine sensitivity of the patient results to

the overall clinic and intervention effects. These analyses will be tabulated and reported by clinic, by intervention, and overall.

## PROTECTION OF HUMAN SUBJECTS

Human subjects protection will be of utmost priority throughout the research study. Study personnel will strictly adhere to policies and regulations as defined and outlined by the Institutional Review Board (IRB) for Protection of Human Subjects of the University of California, San Francisco (UCSF) (Award Number: A122561) and the University of California, Los Angeles (UCLA) (IRB Application still under review as of 4/29/15).

### Potential Risks

Focus groups, interviews and mock pilot testing: Potential risks are low in all three formats. Inadvertent disclosure of patient's condition such as having cervical cancer may cause embarrassment or psychological distress in the focus groups. For the focus groups and interviews, discussion about procedures that previously caused distress may invoke stress. Since these women are volunteers and it will be explained to them ahead of time, it is likely that these risks are extremely low. Women who will try the mock intervention are not likely to have any risks unless as above, it induces stress given a past situation.

*Randomized Intervention Trial:* Risks for participation are low. It is possible that completing the tablet intervention will induce anxiety, however, input from the community stakeholders and patients during the development of the app should keep this to an extremely rare event, if ever. Women do not have to complete the tablet intervention and they can stop it any time. The tablet will be voluntary at the clinic sites. No PHI will be collected from the tablets on the women for this study nor shared with investigators. Data from the tablets is not stored anywhere including the risk assessment. It will be deleted immediately after clients complete the survey.

*Patient Satisfaction Survey:* Risks for participation are low to none. Patients will be asked about age and condition but no personal identifiers will be collected. Information about ease of tablet use will be asked as well as whether the tablet was informative and helpful.

*Protections Against Risk:* For focus groups, women will be asked prior to consenting if they are comfortable talking about their condition (cervical cancer, dysplasia). If they are not, then they will be asked not to disclose any time during the focus groups. All tape-recorded data will be immediately brought back in a locked carrying case to UCSF where it will be stored in a locked cabinet until used for feedback. Some of the discussions may reveal certain sexual behaviors. We will instruct the focus groups that everything said at the focus group is considered confidential and we ask them not to repeat any information shared at the focus group. If anyone feels uncomfortable we will excuse them. In addition, we will make sure that they feel that they do not need to respond to ours or others questions. No individual information will be identified or recorded. Individual interviews will be asked similar questions and tape recording will be handled similarly. If at any time a women appears uncomfortable, we will stop the interview.

*Individual interview and mock intervention:* First, beta form for the intervention will be submitted to the UCSF CHR for final approval prior to testing the version. Upon approval, women who will be asked to perform the mock interventions will be instructed that if they feel at any time uncomfortable with the intervention, they can stop at any time. Also if they have any questions during the intervention, they can ask the study coordinator. Tape recordings will be handled similar as above.

The electronic data sets are protected with a password and stored on a secure network. The servers containing the data are kept in a locked office with limited access inside of a locked suite at the DHCS in Sacramento. All UCSF personnel working with the data have signed confidentiality agreements and completed HIPAA training courses.

### Benefits to Subjects

*Focus groups/interview/mock pilot testing:* no benefits will occur for participating in the study except that the subjects may gain important information regarding cervical cancer screening. Risks to the subjects are low. Inadvertent disclosure of HPV status or cervical cancer status may occur which could cause distress.

*Randomized trial clinics:* Risk to the women is very low since the tablets are informational. In addition, the final intervention will be submitted to the UCSF CHR and UCLA IRB for final approval before moving onto the randomized trial. Women will not be randomized only clinics. Women may benefit since they would have increased education and more satisfaction having knowledge about cervical cancer screening guidelines. Patient may benefit if screening guidelines are adhered to by the provider.

*Patient Satisfaction survey:* No benefit will occur the women for completing the survey.

### Benefits to Society:

The knowledge from the focus groups and interviews will serve the development of the patient intervention tool. This in turn may increase adherence to the US Cervical Cancer Screening (CCS) guidelines and management of abnormal cytology. This in turn would result in decrease invasive procedures for young women. The study may give us insight in to how to assist provider and patients to adhere to the US CCS guidelines. The risks for participation in the focus groups and interviews are low. Information from the trial may give us intervention tools that increase adherence to guidelines by both providers and patients.

